### 13.0 Statistical Considerations

The primary objectives of the statistical analysis will be (1) to demonstrate that there is a population of CLL cells that do not leave or take sanctuary outside of the peripheral blood system in solid lymphoid tissues, (2) to describe the longitudinal pattern in observed labeled cells and (3) to estimate rates of cell death.

For purposes of statistical analysis, the experiment will be divided into two periods (with each period, itself, being divided into two subperiods): Period 1 corresponds to the non-interventional period when heavy water is consumed for 4 weeks (Period 1a) and then discontinued (Period 1b) so that a CLL cell disappearance rate can be tracked over time.

Period 2 corresponds to the interventional period when Btk inhibitor (PCI-32765) is administered to subjects. Assuming that the observed percentage of labeled cells (LC) reaches a peak at some point in time,  $T$ , then Period 2a is defined as the “pre-peak” sub-period (i.e., all times  $t \leq T$ ) and Period 2b is the “post-peak” sub-period ( $t > T$ ).

[figure not shown]
[figure not shown]
Strictly speaking, Period 1 does not enter into any statistical analysis, as it only serves to provide labeling for the cells that allegedly remain and return and are retained in solid tissues. However, Period 1 will permit definition of CLL cell birth rate and disappearance rate (death and permanent return to solid tissue from blood).

An important part of the statistical analysis in Period 2 is characterization of the pattern of LC over time. Patterns will be analyzed both visually and using more formal statistical methods in an exploratory manner. First, the pattern will be smoothed using a cubic spline interpolation (SAS Graph, SAS Institute, Cary, NC). This will facilitate the determination of shape and numbers and patterns of peaks by eliminating “noise” in the data. Second, based on the patterns observed after smoothing, the data will be fit to candidate regression models (e.g., parabolas, mixtures of parabolas, piecewise curves, etc.) and the best fitting model will be identified using common statistical methods such as  $R^2$ , Akaike’s information, etc. All curves will be fit on individual subjects, thereby permitting subjects to vary in the pattern of their LC response curves.

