For example, one possible pattern would be an inverted-U parabola (Figure 1), where LC initially increases (presumably, as previously labeled CLL cells are simultaneously retrieved from solid tissue sanctuaries) and then declines (as the solid tissue sanctuaries have been depleted). Another example would be a mixture of two inverted-U parabolas (Figure 2), whereby there are two distinct peaks, suggesting that retrieval of cells from solid tissue may take place at two distinct times. Clearly, many other patterns are possible; however, the most likely candidate patterns are those with some form of initial upward slope, followed by a global peak, followed by a downward slope.

Interim analyses and stopping rules: In order to monitor study progress and success, interim analyses will be done after the first 5 and the first 10 patients have been labeled and treated for 3 months. The study will be placed on hold if the interim analyses determine that in less than 3 out of 5 patients or in less than 6 out of 10 patients, sufficient kinetic biomarker measurements can be obtained to accomplish the study

objectives (for technical and other reasons, such as patient compliance). In this case, the study would need to be modified and can only be re-opened after a protocol revision that addresses such potential technical and/or logistical issues, which needs to be agreed upon among the Principal Investigators and the sponsor. At that time, the investigators together with the sponsor will determine whether the data indicate that the objectives of the study can be met, or whether substantial changes to the protocol or data analyses would become necessary. This interim analysis will, however, not place the patient accrual on hold, unless the interim analyses would come to the conclusion that the study needs to be modified. In addition, at any time during the trial, if we see more than 30% of patients experiencing grade 3-4 non-hematological toxicities, we will stop the trial.

In general, no formal statistical inference is planned (i.e., hypothesis tests or confidence intervals). The analysis is exploratory with the primary objective of discovering patterns of observed labeling that might provide further insights into the kinetics and biology of CLL.

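### Section 13 relies on an interpolating cubic spline to remove noise before counting peaks, which it cannot do, and sets no selection rule (R-squared is allowed) to repair it

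*Combined protocol and SAP*

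**What the plan says.** Section 13.0 makes describing the longitudinal pattern of labelled cells (LC) the second of its three primary statistical objectives. For Period 2 it sets out these steps:

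- **Smoothing.** "First, the pattern will be smoothed using a cubic spline interpolation". This is meant to "facilitate the determination of shape and numbers and patterns of peaks by eliminating" noise. No smoothing parameter, knots or tolerance are given.
- **Candidate curves.** These are chosen after looking at the smoothed pattern. The list is open and gives parabolas, mixtures of parabolas and piecewise curves as examples.
- **Selection.** "the best fitting model will be identified using common statistical methods such as" R-squared and Akaike's information. Neither is given precedence, and no small-sample correction is mentioned.
- **Unit of fitting.** "All curves will be fit on individual subjects, thereby permitting subjects to vary in the pattern of their LC response curves".
- **Expected shape.** "the most likely candidate patterns are those with some form of initial upward slope, followed by a global peak, followed by a downward slope". If a mixture of two parabolas is seen, "there are two distinct peaks, suggesting that retrieval of cells from solid tissue may take place at two distinct times".
- **Peak time T.** Periods 2a and 2b are split at T: "Assuming that the observed percentage of labeled cells (LC) reaches a peak at some point in time". How T is to be located is not stated.

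Section 13.0 also says that, in general, "no formal statistical inference is planned (i.e., hypothesis tests or confidence intervals" are what it has in mind), and that the work is exploratory.

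**The concern.** Interpolation and smoothing are different operations. An interpolant reproduces each observed value, so measurement error is carried into the curve in full, and the curve can bend between draws as well. The plan assigns to this step the one task it cannot do, which is to separate real peaks from noise.

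The later steps do not repair this. A noise peak seen at the first step can put a two-peak curve on the candidate list. R-squared then never prefers the simpler of two nested curves, and uncorrected AIC protects poorly with so few points per subject.

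At stake is the descriptive product of the study. Section 13.0 reads a rise as retrieval of labelled cells from tissue and, in hedged terms, two peaks as retrieval at two times. With no test or interval behind the description, nothing later would catch a peak made by noise.

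**Working it through.** **The plan's own figures.** The documents give no draw count, assay error or false-peak rate. The one sample-size figure reproduces: 30 x (1 - 0.20 - 0.20) = 18 evaluable. This point does not depend on it.

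**Draws per subject in Period 2** (Sections 8.2 and 8.9: day 1, day 3, week 2, then two-weekly for at least the washout length, then three monthly draws):
- 6-week washout: 2 + 3 + 3 = 8.
- 12-week washout: 2 + 6 + 3 = 11.
- The PCI-32765 Schedule of Events appears to stop these draws at week 12: 2 + 6 = 8.
- Section 14.0 speaks of a 12-16 week delay after labelling. Read literally, 16 weeks gives 2 + 8 + 3 = 13.

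These places need reconciling. The sizes below use 8-11 draws unless stated.

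**Does the spline remove noise?** By definition the interpolant s satisfies s(t_i) = y_i at every draw. Fitted to simulated data on these schedules, its largest residual was below 1e-15.

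**How often does it show a false second peak?** Assumptions: one true peak, parabolic rise and fall, baseline level at first and last draw, peak at 35% or 50% of follow-up, independent multiplicative normal error, and a second peak counted only if its prominence is at least 10% of the fitted curve's range. At 5% CV:

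| True peak above baseline | Interpolating spline, 8-11 draws | REML smoothing spline |
|---|---|---|
| 25-50% | about 14-84% | about 0-3% |
| 100-200% | 0-18% | about 0-3% |

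In each row the upper end comes from 11 draws; on 8 draws alone the interpolant gives 14-52% and 0-4%. More draws mean more chances for a noise peak. Of 18 evaluable subjects, 14-84% is 2.5 to 15.1, and 18% is 3.2.

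Peak height matters because of the ratio of noise to rise. For a 25% peak, the error SD is 0.05 x 1.00 to 0.05 x 1.25, that is 0.050-0.0625, or 20-25% of the 0.25 rise. For a 200% peak it is 0.05-0.15, or 2.5-7.5% of the rise of 2.

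Sensitivity to the assumed CV (all grids, including 13 draws): at 2% the interpolant gives 0-40% (low peaks) and 0-1% (tall peaks); at 10% it gives 49-99% and 8-84%.

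**A second set of assumptions.** With noise SD set to 5-20% of peak height and a prominence rule of 10% of peak height, a single true parabola gave two or more peaks in 5-71% of subjects (8 draws) and 12-95% (11 draws).

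**Does the selection step help?** Compare one parabola (3 coefficients) with a nested continuous two-piece parabola (6, counting the searched knot).
- R-squared: the residual sum of squares (RSS) cannot rise when terms are added. It chose the two-piece curve in 100% of runs.
- AIC prefers two pieces when n ln(RSS1/RSS2) > 2 x 3, so when RSS1/RSS2 > exp(6/n). That is exp(0.75) = 2.1 at 8 draws and exp(0.545) = 1.7 at 11. With one true parabola it chose two pieces in 47-56% of runs on 8-11 draws.
- AICc adds 2k(k+1)/(n-k-1), with k = 4 and 7 once the variance is counted. At n = 8 the second divisor is 8-7-1 = 0, so it is undefined. At n = 11 the terms are 40/6 = 6.67 and 112/3 = 37.33, and the required ratio is exp((6 + 30.67)/11) = 28.

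A chosen two-piece curve is not always two visible peaks. With both vertices required inside the follow-up, the 10% rule, 5% CV and a flat or one-peak truth, two peaks were reported in 0-31% (R-squared) and 0-22% (AIC) across the grids.

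**The case against.** - **The wording may just be loose.** Smoothing and interpolation contradict each other in one sentence, and a smoothing spline may have been meant. If so, the false-peak rates for the interpolant fall away. Section 13.0 would still need correcting, because the wording would be wrong and the smoothing parameter missing.
- **The sizes rest on assumptions.** This stands. Assay error is not given, the 10% rule is a reviewer's choice, and patterns will also be judged by eye, so tiny wiggles would not be reported. Under a 25% rule at 5% CV the interpolant gives 1-15% for 50% peaks and 0-3% for 100-200% peaks, though still 17-64% for 25% peaks.
- **The consequence is limited.** This also stands. No test, stopping rule or sample size uses the peak count, and the two-peak reading is hedged.

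Four stronger readings are tempting but not supported:
- *R-squared alone decides.* Akaike's information is named beside it, and the nesting argument applies only to nested candidates.
- *Flat or monotone curves are ruled out.* The list is open, and a parabola with its vertex outside the sampling window is monotone. They are merely not named.
- *Subjects have up to 13 draws, so the problem is larger.* On 11-13 draws the upper ends would be 94% and 40%, but 13 rests on one reading of Section 14.0.
- *T is the observed maximum, so noise alone creates a false pre-peak rise.* The plan defines T only on the assumption that a peak exists and does not say how it is found. This is a gap to fill, not a demonstrated bias.

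**Conclusion.** The concern holds. The statement that cubic spline interpolation eliminates noise is false as written; this follows from the definition and needs no simulation. Nothing later in Section 13.0 reliably corrects it, because candidates are drawn from the interpolated picture and no selection rule is fixed.

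The practical size is conditional on assay precision and peak height. It is material for low peaks at an assumed 5% CV and small for tall peaks with a precise assay. The draw count of 8-11 follows Sections 8.2 and 8.9.

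This should be changed, but it does not invalidate the study. The exploratory label limits what follows from a false peak. It does not excuse the method, because describing the pattern is itself a primary statistical objective.

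**What to change.** In Section 13.0:

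1. Replace the interpolating spline with a smoothing spline whose penalty is set by REML, named in advance. Delete the statement that interpolation eliminates noise.
2. Drop R-squared as a selector. List flat and monotone curves among the candidates. Name in advance one criterion that is defined for every candidate, and use it for all candidates in all subjects. Leave-one-out cross-validation is one option. If AICc is preferred, restrict the candidates to those for which it is defined. Do not switch between the two, because their scores are not comparable.
3. Show any second peak from the smoothed curve as descriptive, without barring it.
4. State that T is taken from the fitted curve and is undefined when that curve is flat or monotone.

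Also reconcile the sampling period across Sections 8.2, 8.9 and 14.0 and the Schedule of Events.

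**Cost.** SAP wording and modest programming; no extra samples or patients. Some real low or second peaks will be missed:
- On 8 draws, 5% CV and a true peak 25% above baseline, AICc finds the peak in 38-52% of subjects and leave-one-out in 91-97%.
- Leave-one-out pays for this with false rises in 18-25% of flat subjects, against 2-7% for AICc.
- On 8-11 draws a true second peak (two equal humps, assumed; 5% or 10% CV) is selected in only 0-1% (AICc) or 0-20% (leave-one-out), while the REML curve shows it in 12-100% across the grids. That is why second peaks should stay visible as description.

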## **2.0 Background**

### 2.1 Chronic Lymphocytic Leukemia (CLL)

CLL is the most common form of adult leukemia in the United States. It has been estimated that there are approximately 150,000 individuals living with CLL in the United States. The use of chemoimmunotherapy as initial therapy is associated with high response rates, but this therapy is less effective and displays more side effects in elderly subjects. Once disease relapse has occurred after chemoimmunotherapy, second line treatment is less effective and response durations are shorter. An alternative to repeating chemoimmunotherapy is to use the monoclonal antibody (mAb) alemtuzumab. Alemtuzumab can induce a therapeutic response in up to 30% of subjects, but is associated with significant immunosuppression and infections; also, it lacks activity in subjects with bulky lymphadenopathy (larger than 5 centimeters;. Combinations of purine-analogue based regimens have limited activity, and once subjects are fludarabine refractory their median survival is <12 months based on published experience.

Kinase inhibitors affecting signaling of the BCR, such as PCI-32765, are an alternative, targeted therapeutic approach for relapsed and elderly CLL subjects, based on promising results in early-phase clinical trials and lack of toxicities. Characteristically, treatment with PCI-32765 induces a rapid reduction in lymphadenopathy, which is accompanied by a transient lymphocytosis; the latter is thought to be due to re-distribution of CLL cells from tissues into the peripheral blood. Then, inhibition of BCR-related survival signaling by PCI-32765 causes “starvation” and a slow-onset, continuous reduction of the leukemia cell burden over time. These mechanisms of action have not been formally demonstrated *in vivo*. Labeling of the DNA of newly-born CLL cells with deuterium (H), administered in the form of H2O prior to therapy with PCI-32765, will allow us to determine the effects of PCI-32765 on leukemia cell mobilization from tissues into the peripheral blood, and on leukemia cell kinetics (proliferation, survival, and cell death).

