### **8.9 Sample Collections for H-DNA-labeled Leukemic Cells during PCI-32765 Treatment Phase**

After beginning PCI-32765 therapy, subjects will be seen for follow-up visits including blood draws (60ml) at day 1 (+/- 3 days), day 3 (+/- 1 day), week 2 (+/- 3 days), and every 2 weeks (+/- 3 days) thereafter for a period at least equal in duration to that of the initial H2O washout phase of 6 to 12 weeks. At these visits, clinical and laboratory assessment, which will include blood sampling (60ml) for H2O kinetic measurements, will be made. Subjects will continue to return or be seen by a local physician or clinical laboratory each month (+/- 3 days) for an additional 3 months for blood drawing (60ml). Data obtained from these blood samples will permit a determination of the slope and rate of the appearance of previously labeled CLL cells in the blood, and the slope and rate of the disappearance of labeled cells from the blood. If re-circulation to solid tissues is inhibited by PCI-32765 therapy, the disappearance rate will represent primarily the death rate of leukemic cells *in vivo*. Because during the treatment period, H2O will not be available to label newly-born cells, any cells containing H-labeled DNA will represent cells labeled during the initial period of H2O consumption and retained *in situ*. The kinetic measurements of the entire CLL clone will be compared with those of intracлонаl fractions from the same samples, defined by the reciprocal differences in CXCR4/CD5 surface membrane densities; this approach is described in the published study by Calissano et al. (Mol Med 2011;17: 1374-1382, 2011). In addition, these fractions will be analyzed for:

1. Phenotype and numerical changes of B and T cells and myeloid cells within these fractions, pre- and post-ibrutinib therapy
2. Gene expression profiles of cells within these fractions, pre- and post-ibrutinib therapy
3. DNA methylation profiles of cells within these fractions, pre- and post-ibrutinib therapy.

4. Response to BCR and other signals of cells within these fractions, pre- and post-ibrutinib therapy, using western blots on phosphoproteins/ibrutinib occupancy
5. Differences in engraftment and growth capacities of CLL B and T cells in NSG mice, unseparated or within these fractions, pre- and post-ibrutinib therapy

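### The plan promises appearance, disappearance and death rates for labeled cells, but none of the Period 2 curves it names has a rate constant

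*Combined protocol and SAP*

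**What the plan says.** Section 13.0 lists three aims for the analysis, the third being to estimate rates of cell death. For labeled cells, Section 8.9 says the on-treatment samples will give "the slope and rate of the appearance of previously labeled CLL cells in the blood, and the slope and rate of the disappearance". It adds that if return to tissue is blocked, the disappearance rate mainly reflects death.

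For the Period 2 curves, Section 13.0 smooths each subject's series with a spline and then says "the data will be fit to candidate regression models (e.g., parabolas, mixtures of parabolas, piecewise curves, etc". Selection is by fit: "the best fitting model will be identified using common statistical methods such as" R-squared and Akaike's criterion. Both worked examples are parabolas: "one possible pattern would be an inverted-U parabola (Figure 1" and "Another example would be a mixture of two inverted-U parabolas (Figure 2". The text then leaves the list open: "Clearly, many other patterns are possible". T, the peak of the observed labeled percentage (LC), divides Period 2a from Period 2b.

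No exponential or compartment form is named, and no section says how a fitted curve becomes a rate.

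**The concern.** A rate of appearance or loss is a proportion per unit time. A straight segment has a slope in percentage points per day, and its proportional rate changes as the level changes. A parabola's slope changes at every point. Neither gives one number per subject that can be called a loss rate, so a primary aim has no stated estimator.

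Two consequences follow. First, if a segment slope stands in for the rate, its value depends on how long the subject was followed. Follow-up is not common to all subjects: two-weekly sampling lasts 6 to 12 weeks, matching each subject's own washout, and three monthly draws follow. Second, a parabola is symmetric about its vertex. Section 2.1 expects rapid nodal shrinkage with lymphocytosis and then "a slow-onset, continuous reduction of the leukemia cell burden over time". If LC behaves similarly, a parabola's vertex is drawn towards the middle of the sampling window. If that vertex were used as T, weeks of decline would be counted as release.

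**Working it through.** The documents give no peak day, release rate, loss rate or noise level for Period 2, so there is no figure to reproduce. The sizes below rest on assumed values.

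**Draw times (Section 8.9).** Days 1 and 3, week 2, then every 2 weeks for 6 to 12 weeks, then three monthly draws. Counting from first dose, 12 weeks gives t = 0, 2, 14, 28, 42, 56, 70, 84 (8 draws). Monthly draws add 112, 140, 168 (11 draws). A 6-week schedule has 5 draws; its monthly draws fall at 70, 98, 126 (8 draws).

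**Assumed response.** LC(t) = 8 + C[exp(-k1 t) - exp(-k2 t)], with k1 = ln 2 / loss half-life, k2 set so that the peak falls on the chosen day, and C set so that the rise is 4 points. For peak day 14 and half-life 56 days: k1 = 0.693/56 = 0.0124 per day, k2 = 0.217 per day, C = 4/(0.841 - 0.048) = 5.04.

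**Step 1: does a segment slope act as a rate?** Best two-segment line, free knot, no noise, peak day 14, half-life 56 days:
- to week 12: -0.032 points per day
- 6 weeks plus monthly draws (to day 126): -0.027
- 12 weeks plus monthly draws (to day 168): -0.022

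The true k1 is 0.0124 per day in all three. Follow-up length alone changes the slope by a factor of 0.0323/0.0220 = 1.47 between weeks 12 and 24, and by 0.0268/0.0220 = 1.22 between the shortest and longest full schedules.

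**Step 2: where does a single parabola put the peak?** Least squares for a + bt + ct², vertex -b/(2c), no noise; lateness = (vertex - true peak)/7.

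| True peak, half-life | Vertex to week 12 | Vertex to week 24 |
|---|---|---|
| day 14, 56 d | day 42.0 (4.0 weeks late) | day 54.4 (5.8) |
| day 21, 56 d | day 44.3 (3.3) | day 64.3 (6.2) |
| day 28, 84 d | day 48.3 (2.9) | day 76.5 (6.9) |
| day 14, 84 d | day 44.7 (4.4) | day 66.3 (7.5) |

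A second family, decaying to zero with release half-life 1 to 7 days and loss half-life 30 to 120 days, gave vertices 0.5 to 5.0 weeks late in all 12 scenarios on the 12-week schedule. With the monthly draws added, 7 of 12 were late by 0.7 to 7.2 weeks, and in 5 the parabola had no peak in the window.

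**Step 3: would the plan's selection rule keep the parabola?** In the four curves of the table, parabola R-squared is 0.34 to 0.82, against at least 0.96 for the two-segment line. With noise SD 0.25 or 0.5 points, AIC chose the two-segment line in 93.5 to 100% of simulated subjects. Small-sample AICc at 8 draws chose it in only 17 to 92%, but at 11 draws every time. The knot itself falls early: day 5 when the true peak is day 14.

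**Step 4: does an exponential form recover the rate?** Baseline plus difference of two exponentials: median estimated loss rate 0.97 to 1.08 times truth. At 8 draws individual estimates are imprecise: the 10th to 90th percentile was as wide as 0.36 to 2.3 times truth in one set of simulations and 0.27 to 3.2 in another. For the second family, a log-linear fit from day 28 on 12 weeks of data returned a median of 0.0103 to 0.0117 per day for a true ln 2/60 = 0.0116.

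**The case against.** A reader might infer that the plan commits itself to parabolas and will therefore place peaks weeks late. The documents do not support that. The list is a set of examples, includes piecewise curves, ends open and selects by fit; Step 3 shows the parabola would usually lose. T is worded as the peak of the observed percentage. In noisy simulations the median observed maximum was day 14 for a true peak at day 14, and day 28 for true peaks at days 21 or 28. The late-peak figures mostly describe a fit the plan would discard. They matter only if a parabola wins, as it can under AICc with 8 draws, and its vertex is then used as T.

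It is also fair that Section 2.1 describes amounts of leukemia, not the labeled percentage, so a fast-rise, slow-fall LC curve is an assumption. An open list could admit exponential segments, and piecewise segments do give slopes, which Section 8.9 also asks for. Section 13.0 calls the work exploratory, with no formal inference.

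A four-parameter curve on 5 to 11 draws is fragile, and a single-release form cannot show the two-peak pattern that Section 13.0 wants to detect. This argues against making it the sole curve. It does not supply the missing estimator: exploratory status excuses the absence of tests, not the absence of a definition for a rate that is a primary aim.

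**Conclusion.** The point holds as a gap between aims and method. Rates of death, appearance and disappearance are promised, but no named curve family carries a rate constant and no rule derives a rate or T from the chosen curve. The nearest substitute, a segment slope, moves by a factor of about 1.2 to 1.5 with follow-up length alone in the illustrated case. The misplaced peak (about 3 to 7 weeks under the assumed half-lives, less in milder settings) is a conditional risk and not the main defect. A reader might also infer that the data cannot yield rates. That goes too far: an exponential fit to the planned draws recovers them on average. All sizes rest on assumed half-lives, amplitude and noise; mixtures of parabolas were not fitted.

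**What to change.** In Section 13.0:
- Add to the candidates a baseline plus a difference of two exponentials, with one appearance rate and one loss rate. Use a single exponential when no rise is seen or the fit does not converge; it gives a loss rate only.
- Take the appearance and loss rates from that fit, in units per day.
- State whether T is the observed or the fitted peak.
- Keep parabolas, mixtures and piecewise curves for describing shape and number of peaks.

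The fitted loss rate remains a disappearance rate; reading it as death still needs Section 8.9's condition that return to tissue is blocked.

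The cost is analysis wording and nonlinear fitting, with no new samples or visits. In some subjects with few draws the rates will be imprecise or the fit will fail; report these cases as such.

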### **8.2 Heavy Water Protocol: Resting phase.**

At the end of the 4th week, subjects will stop drinking  $^2\text{H}_2\text{O}$  (washout phase) and be followed for 6-12 weeks until beginning treatment with PCI-32765. During the period until initiation of therapy, subjects will be seen every 2 weeks (+/- 3 days) for follow-up visits with clinical and laboratory assessment. Blood will be drawn at the same time every 2 weeks (+/- 3 days), to determine a disappearance rate (death plus re-distribution into solid tissue) of CLL cells containing  $^2\text{H}$ -labeled DNA. Only those subjects that have not imbibed  $^2\text{H}_2\text{O}$  for at least 6 weeks from the end of the labeling period until starting on treatment with PCI-32765 or those patients who have not imbibed heavy water for less than 6 weeks and have received study PI approval will be included in further  $^2\text{H}_2\text{O}$  kinetic studies, although they will receive PCI-32765 as a part of the response to therapy studies. After start of treatment with PCI-32765, there will be blood sampling (60ml) for CLL cell kinetic measurements (heavy water testing) on days 1 (+/- 3 days), 3 (+/- 1 day), and then at week 2 (+/- 3 days) and every 2 weeks (+/- 3 days) thereafter for a period of at least equal in duration to that of the initial  $^2\text{H}_2\text{O}$  washout phase (6 to 12 weeks). Patients will continue to return to clinic each month for blood drawing (60ml). Data obtained from these blood samples will permit a determination of CLL birth rate as well as a slope of labeled cell emergence from solid tissue into the peripheral blood.

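### Section 13 analyses the labelled-cell percentage (LC) alone, and LC alone cannot identify retrieval of cells from tissue or depletion of tissue

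*Combined protocol and SAP*

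**What the plan says.** Section 13.0 builds the Period 2 analysis on one variable: "Assuming that the observed percentage of labeled cells (LC) reaches a peak at some point in time". That peak divides the period into two subperiods, and curves are fitted to each subject's LC. In the inverted-U example the shape is one "where LC initially increases (presumably, as previously labeled CLL cells are simultaneously retrieved from solid tissue sanctuaries) and then declines (as the solid tissue sanctuaries" being by then empty). For a curve with two peaks the text adds "suggesting that retrieval of cells from solid tissue may take place at two distinct times". It expects that "the most likely candidate patterns are those with some form of initial upward slope, followed by a global peak, followed by a downward slope", after conceding "Clearly, many other patterns are possible". No meaning is attached to an LC that stays flat or falls from the first dose. The analysis is declared exploratory, without tests or confidence intervals.

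Section 8.9 says that on treatment "any cells containing 2 H-labeled DNA will represent cells labeled during the initial period of" heavy water intake and retained in situ. Section 8.2 samples blood every 2 weeks between the end of labelling and first dose "to determine a disappearance rate (death plus re-distribution into solid tissue) of CLL cells containing" labelled DNA.

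Section 13.0 names no analysis of absolute labelled-cell numbers. The on-treatment marrow samples in Section 7.0 are for morphology, flow cytometry and residual disease; no deuterium assay of tissue is stated.

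**The concern.** LC is a ratio. Released tissue cells enter its numerator and its denominator, and Section 2.1 expects a lymphocytosis, so the denominator will move. The secondary objective in Section 4.0 treats the mix of recently born and older cells among those mobilised as unknown. The plan therefore cannot presume that released cells are more heavily labelled than those already in blood, yet that presumption is what makes a rise in LC the signature of retrieval.

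At stake are the trafficking half of the primary objective and the first statistical aim in Section 13.0, which concerns cells that do or do not take sanctuary in tissue. A subject with large redistribution and similar labelling in blood and tissue would show nothing on LC. A subject with modest redistribution and a large label difference would look strongly mobilised. Differences in LC pattern between subjects would partly reflect birth rate and exchange rate, not the drug.

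**Working it through.** The plan has no figure of its own to reproduce here. The check is a mass balance followed by illustration.

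**1. Effect of release alone.** Let blood hold B cells with label share p_b, and let the drug release M tissue cells with label share p_t.

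LC after − LC before = (p_b·B + p_t·M)/(B + M) − p_b = [M/(B + M)]·(p_t − p_b).

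The sign is that of p_t − p_b. M sets only the size. This needs no assumed rates.

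**2. Other terms.** With release rate m, tissue and blood pools N_T and N_B, loss rates d_L (labelled) and d_U (unlabelled), and unlabelled births b per blood cell:

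dp_b/dt = m·(N_T/N_B)·(p_t − p_b) − b·p_b − (d_L − d_U)·p_b·(1 − p_b).

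The same balance is applied in the runs below, with births placed in tissue, where they lower p_t.

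**3. Same mobilisation, different labelling.** Assumed, because the documents give no values: blood LC 10% at first dose, tissue pool 3 times blood, release 5%/day, death 1%/day for all cells, no births. Labelled count is indexed to 100 at first dose.

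| Tissue label share | LC day 3 | LC day 14 | LC day 28 | LC day 84 | Labelled count day 28 |
|---|---|---|---|---|---|
| 20% | 12.9% | 16.0% | 16.9% | 17.5% | 417 |
| 10% | 10.0% | 10.0% | 10.0% | 10.0% | 246 |
| 5% | 8.5% | 7.0% | 6.5% | 6.3% | 161 |

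Total blood cells rise 2.46-fold by day 28 in every row. In the first row tissue is more than 99% emptied by day 84 (3.0 to 0.019) and LC still has not turned down, so depletion alone produces no falling limb.

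**4. A fall without depletion, and movement without mobilisation.**
- Tissue 20%, labelled loss 2%/day against 1%/day unlabelled: LC peaks at 14.2% near day 13 and then declines, although 1.261/3.0 = 42% of the tissue pool remains at day 14.
- Tissue 12%, births of 1.7%/day in tissue: LC peaks at 10.6% near day 7 and is 9.9% at day 28, with 0.9/3.0 = 30% of the tissue pool remaining.
- Tissue 12%, labelled loss 3%/day against 1%/day: LC falls to 6.8% by day 28, although tissue began more heavily labelled than blood.
- No mobilisation: LC falls from 10.0% to 4.6% by day 84 if labelled cells die at 2%/day and unlabelled at 1%/day, and rises to 20.5% if the rates are exchanged.

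**5. How often, under the protocol's birth rates.** From the documents: birth rates 0.1, 0.35 and 1.7%/day (Section 2.4), 28 days of labelling (8.1), rest of 42 or 84 days (8.2). Assumed: steady state, births in tissue, equal death in both compartments, tissue:blood ratio 1, 3 or 10, return from blood to tissue 0, 0.02, 0.1 or 0.5/day, 30% of tissue cells released at first dose, full labelling efficiency. That is 3 × 3 × 4 × 2 = 72 scenarios.

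| Birth rate | LC up > 0.5 points | within 0.5 points | down > 0.5 points |
|---|---|---|---|
| 0.1%/day | 7 | 17 | 0 |
| 0.35%/day | 8 | 16 | 0 |
| 1.7%/day | 0 | 8 | 16 |
| All | 15 | 41 | 16 |

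Example: 1.7%/day, ratio 3, return 0.02/day, 84-day rest. Then p_b = 13.2%, p_t = 7.7%, B = 1, M = 0.3 × 3 = 0.9. The change is (0.9/1.9) × (7.7 − 13.2) = −2.6 points, so LC drops to 10.6%. The labelled count goes from 0.132 to 0.132 + 0.9 × 0.077 = 0.201, a 1.5-fold rise.

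**6. Section 8.9.** With no tissue compartment and no drug effect, the labelled share still in blood is (1 − e^(−28b))·e^(−b·rest): 2.6%, 8.1% and 18.5% after 42 days at the three birth rates, and 2.5%, 7.0% and 9.1% after 84 days. Labelled cells on treatment are expected with or without a reservoir.

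**The case against.** Section 13.0 does not lay down a decision rule. The inverted U is an example, the attribution to tissue is marked as a presumption, other shapes are allowed, curves are fitted subject by subject, and no inference is planned. All of that stands. It bears on how heavily to weigh the point, not on whether LC can support the reading. No other route from the data to the tissue-sanctuary aim is written down.

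Three stronger readings are tempting and not supported.
- A reader might infer that the plan would read an LC falling from first dose as depletion. Section 13.0 attaches depletion only to the decline that follows a rise; an initial fall gets no reading.
- A reader might infer that LC's direction depends only on tissue versus blood labelling. That holds for the release term alone, as steps 2 and 4 show.
- A reader might count every scenario in which LC does not rise, which gives 51 of 72, and call them falls. At 0.1%/day the largest fall is 0.02 points and at 0.35%/day it is 0.22 points. Those are flat curves.

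The plan also has related information: lymphocytosis from blood counts, nodal size from CT, and the CXCR4/CD5 fractions in Section 8.9. These help to show that redistribution occurred. Section 13.0 does not combine any of them with LC, so they do not repair its reading.

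**Conclusion.** The concern holds as a limit on interpretation. LC alone cannot identify retrieval from tissue or depletion of tissue. The same true mobilisation can raise it, leave it flat or lower it, a decline after the peak need not mean depletion, and two peaks need not mean two retrieval times. The sign result for the release term is exact. The 15, 16 and 41 of 72 are illustrative: they depend on the assumed pool ratios, return rates and 30% release, and on the 0.5-point cut, which is wide relative to LC at the lowest birth rate. Marked falls appear only at the top of the protocol's birth-rate range; elsewhere the risk is a flat curve being taken as no mobilisation.

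The Section 8.9 statement conflicts with Section 8.2, which follows labelled cells still circulating up to first dose. Because the analysis is exploratory, this is a change that should be made, not one that invalidates the study.

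**What to change.** **Section 13.0.**
- Beside LC, analyse labelled cells per µL (LC × CLL count) and unlabelled cells per µL ((1 − LC) × CLL count) at each kinetic draw with a same-visit blood count. Take the CLL count from flow cytometry where available; otherwise use the absolute lymphocyte count as a stated proxy.
- Read drug-related retrieval as a labelled count above that subject's own Period 1b trend projected forward. A fixed pre-dose value looks simpler but is not conservative: in about 20 of the 72 scenarios the untreated labelled count keeps rising after the first-dose date, by up to 1.46-fold at day 28 and 2.29-fold at day 84 (0.1%/day, ratio 10, no return, 42-day rest). Excluding the roughly 20% with delayed release (Section 14.0) may remove some such subjects but does not make a fixed value safe.
- Amend the sentence that keeps Period 1 out of the statistical analysis, since its trend becomes the reference.
- Keep LC as a descriptive curve. State that a flat or falling LC does not exclude mobilisation and that a decline after the peak need not mean depletion.

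**Section 8.9.** Replace *retained in situ* with: either still circulating at first dose or released from tissue.

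**Cost.** Wording and a simple derived variable; no added subjects or procedures. Counts bring their own measurement error. The projected trend rests on few points: with counts every 4 weeks after day 28, a 6-week rest gives about three (days 28, 56 and first dose) and a 12-week rest about four (days 28, 56, 84 and 112). By the text of Section 10.0 there is no blood count on treatment at day 3, week 6 or week 10, so the count reading is limited to the other draws. Check this against the schedule of events, because Section 8.9 also mentions laboratory assessment at these visits.
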